10.6. Safety and Other Assessments

Safety assessments will include monitoring of AEs, functional recovery assessments, wound complications, length of hospital stay, blood loss, and transfusions.

Adverse events will be monitored by the observations of the principal investigator and medical staff and/or spontaneous reporting throughout the study.

10.7. Adverse Events and Serious Adverse Events

10.7.1. Definitions

Adverse Event – Any untoward medical occurrence in a clinical investigation subject administered a drug and does not necessarily have a causal relationship with this treatment. An AE can therefore, be any unfavorable and unintended sign (including an abnormal laboratory finding), symptom, or disease temporally associated with the use of an investigational product, whether or not related to the investigational product.

Suspected Adverse Reaction – any adverse event for which there is a reasonable possibility that the drug caused the adverse event. For the purposes of IND safety reporting, "reasonable possibility" means there is evidence to suggest a causal relationship between the drug and the adverse event. Suspected adverse reaction implies a lesser degree of certainty about causality than adverse reaction, which means any adverse event caused by a drug.

Serious Adverse Event (SAE) – Any experience that is fatal or life-threatening, requires or prolongs inpatient hospitalization, results in persistent or significant incapacity or substantial disruption of the ability to conduct normal life functions, is a congenital anomaly or birth defect, or an important medical event that, based upon appropriate medical judgment, may jeopardize the subject and may require medical or surgical intervention to prevent one of the outcomes listed in this definition.

Unexpected Adverse Event/Suspected Adverse Reaction – Any adverse event or adverse reaction that is not identified in nature, severity, or frequency in the Product Labeling.¹

10.7.2. Classification of an Adverse Event

The Principal Investigator will evaluate all AEs as follows:

Seriousness: whether or not the AE is fatal or life threatening, persistent or permanently disabling, requires or prolongs inpatient hospitalization, is a congenital anomaly or an important medical event or requires medical intervention to prevent one of the above outcomes

Action taken: whether or not the AE caused the subject to discontinue the study drug, or use a concomitant medication

Intensity, to be graded as:

DEGREE	DESCRIPTION
Mild	Awareness of signs and symptoms; easily tolerated
Moderate	Discomfort sufficient to interfere, but not prevent daily activity
Severe	Unable to carry out usual activity

Relationship to study drug, to be graded as:

DEGREE	DESCRIPTION
Not related	The experience is clearly related to other factors such as the subject's clinical state, therapeutic interventions or concomitant drugs administered to the subject.
Unlikely	The experience was most likely produced by other factors such as the subject's clinical state, therapeutic interventions or concomitant drugs administered to the subject which do not follow a known response pattern to the trial drug.
Possible	The experience follows a reasonable temporal sequence from the time of drug administration, and/or follows a known response pattern to the trial drug, but could have been produced by other factors such as the subject's clinical state, therapeutic interventions or concomitant drug administered to the subject.
Probable	The experience follows a reasonable temporal sequence from the time of drug administration, and follows a known response pattern to the trial drug, and cannot be reasonably explained by other factors such as the subject's clinical state, therapeutic interventions or concomitant drugs administered to the subject

Related
	
The experience follows a reasonable temporal sequence from the time of drug administration, and follows a known response pattern to the trial drug, and cannot be reasonably explained by other factors such as the subject’s clinical state, therapeutic interventions or concomitant drugs administered to the subject, and either occurs immediately following trial drug administration, or improves on stopping the drug, or reappears on repeat exposure, or there is a positive reaction at the application site.

----------------	---

10.7.3. Adverse Event and Pregnancy Follow-Up

The Investigator should take all appropriate measures to ensure the safety of the subjects, including referral to a specialist if indicated. The Investigator should follow up on the outcome of any AE (including SAEs) until the event has resolved or stabilized, or until 30 days from the initial report of the AE, whichever occurs first.

Any pregnancy that occurs in a subject or the partner of a subject on study drug must be reported to the Sponsor within 24 hours of learning of its occurrence. The pregnancy should be followed up to determine outcome, including spontaneous or voluntary termination, details of the birth and presence or absence of any birth defects, congenital abnormalities or maternal and/or newborn complications.

Any SAE brought to the attention of the Investigator within 30 days after cessation of study drug should be reported through the SAE reporting process.

10.7.4. Adverse Event Reporting

Any AE (clinical sign, symptom, or disease) temporally associated with the use of this investigational product, whether or not considered related to the investigational product, should be documented on the source document. All AEs reported by the subject or observed by the Principal Investigator will be individually listed. The signs and symptoms, time of onset (24-hour clock), duration, action taken and follow-up procedures will be reported.

10.7.5. Serious Adverse Event Reporting

The Principal Investigator shall document all AEs. He/she must report (by phone, email, etc.) any SAE to the Sponsor or its designee and to any IRB (Institutional Review Board) that has reviewed and is continuing to review the investigation within 24 hours of the first knowledge of the occurrence.

Fatal or life-threatening occurrences in clinical investigations qualify for very rapid reporting. Regulatory agencies should be notified (e.g., by telephone, facsimile transmission, or in writing) as soon as possible but no later than 7 calendar days after first knowledge by the sponsor.

Serious adverse events that are not fatal or life-threatening must be filed as soon as possible but no later than 15 calendar days after first knowledge by the Sponsor that the case meets the minimum criteria for expedited reporting.

For any SAE, the Principal Investigator must notify the contact persons listed below within 24 hours:

Sponsor contact information

[name]
[name]
[contact] [name]
Email: [contact]

[name], MBA
[name]
[contact] [name] [contact]
Email: [contact]

Principal Investigators will be responsible for reporting any SAEs to the Sponsor, who report them to the FDA.

11. STATISTICAL CONSIDERATIONS

11.1. Statistical Hypothesis

The null hypothesis (H0) is that there is no difference between the two groups. The alternative hypothesis (H1) is that the two groups are significantly different.

11.2. Sample Size Determination

Assuming a two-sided alpha level of 0.05, 80% power and estimated mean blood loss of 2000 mL in the control group (with a relatively low estimated standard deviation of 1000 mL due to limitations in the type of surgery and the patient population) a 25% decrease in blood loss in the treated group would require 128 patients (64 per group). Thus, the proposed sample size of 150 patients (100 active and 50 placebo) will allow 14.7% loss to follow-up which should be sufficient considering the relatively small likelihood of loss to follow-up in these patients.

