5. SCHEMATIC OF STUDY DESIGN

CP-006-2017 – Efficacy and safety of tranexamic acid in spinal fusion surgery

- ❖ Study Cohort - > Adult patients over age 18 electively undergoing complex spinal fusion surgery (T2 to pelvis/Sacrum, greater than 4 FSU's (5 vertebral segments or more)).
- ❖ Arm 1 - > Subjects receiving study drug (treat) (n = 100).
- ❖ Arm 2 - > Subjects receiving placebo (control) (n = 50).
- ❖ Sample size - > 150 study subjects; randomized 2:1 Treat / Control
- ❖ Intervention: Arm1 – Surgery plus study drug
Arm 2 – Surgery with placebo

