11.4.2. Analysis of Primary Efficacy Endpoint(s)

The primary efficacy variable will be total blood loss as described in Section 10.1. Since blood loss will be measured up to 24 hours after surgery and over the entire period of hospitalization, the primary measure will be the 24-hour level. Blood loss at later time-points will only be considered significant if the 24-hour measure has also reached statistical significance. Due to the hierarchical structure of this analysis, no adjustment for multiplicity will be performed.

The primary efficacy variables and continuous secondary efficacy variables will be analysed using Analysis of Covariance (ANCOVA) where one factor is treatment (TXA vs Placebo) and the other factor is Surgeon. The initial analysis will include the interaction between the

two factors in order to assess the similarity of effects across surgeons. Significant interaction effects will occur if (for example), TXA works for some surgeons but not for others. The final efficacy analysis will remove the interaction term and control for overall differences between surgeons.

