11.4.9. Exploratory Analysis

Exploratory subgroup and covariance analyses may also be performed

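### The 128-patient requirement assumes equal arms, but the trial randomises 2:1; after the stated 14.7% loss power is about 75.5%, not 80%

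*Combined protocol and SAP*

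**What the plan says.** Section 11.2 sets out the inputs: "Assuming a two-sided alpha level of 0.05, 80% power", an "estimated mean blood loss of 2000 mL in the control group", a "relatively low estimated standard deviation of 1000 mL", and a 25% reduction under treatment. It concludes that these "require 128 patients (64 per group). Thus, the proposed sample size of 150 patients (100 active and 50 placebo) will allow 14.7% loss" to follow-up, and judges that margin sufficient because few patients are likely to be lost.

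Section 5 confirms the allocation: "150 study subjects; randomized 2:1 Treat / Control", with 100 in the active arm and 50 in the placebo arm.

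Section 11.4.2 names an analysis of covariance in which "one factor is treatment (TXA vs Placebo) and the other factor is Surgeon". No baseline covariate is listed. Covariate analyses appear only as an option in Sections 11.4.7 and 11.4.9: "Exploratory subgroup and covariance analyses may also be performed".

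**The concern.** Section 11.2 changes design partway through its argument. The requirement is worked out for two arms of 64. The total of 128 is then subtracted from a trial of 100 and 50, and the remainder is presented as tolerable loss. The planned placebo arm of 50 is below the 64 per group before anyone is lost, and nothing in the section adjusts for the unequal split.

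Total blood loss is the first primary endpoint, and Section 7 says the trial is meant to support registration. If the permitted attrition occurred, the trial would run below its stated power on that endpoint while the protocol said otherwise. Anyone using Section 11.2 to decide how much missing data is acceptable would be working from a margin more than three times too wide (14.7% against 4.0%).

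**Working it through.** **Inputs (Section 11.2 unless noted).** Two-sided alpha 0.05; power 80%; control mean 2000 mL; reduction 25%, so the difference is 0.25 × 2000 = 500 mL; SD 1000 mL, taken as common to both arms; standardised difference d = 500/1000 = 0.5; 100 active and 50 placebo; allocation 2:1 (Section 5).

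**Method.** Two-sample t-test. The noncentrality is d / √(1/n₁ + 1/n₂) on n₁ + n₂ − 2 degrees of freedom, and power comes from the noncentral t distribution.

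**Step 1: reproduce the plan's figures.**
- 63 + 63: power 79.5%.
- 64 + 64: 1/64 + 1/64 = 0.03125, noncentrality 0.5/√0.03125 = 2.83, power 80.1%.
- Loss allowance: (150 − 128)/150 = 22/150 = 14.67%.

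So 128 and 14.7% both reproduce, the first only with equal arms.

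**Step 2: apply the same 128 at 2:1.** With loss in proportion, 85 + 43 remain: 1/85 + 1/43 = 0.03502, noncentrality 0.5/√0.03502 = 2.67, power 75.5% (76.2% by the normal approximation).

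**Step 3: find the 2:1 requirement.** With 96 + 48, 1/96 + 1/48 = 3/96 = 0.03125, exactly the variance factor of 64 + 64. So 144 patients at 2:1 do the work of 128 at 1:1.

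| Evaluable (active + placebo) | Total | Power (t-test) |
|---|---|---|
| 64 + 64 | 128 | 80.1% |
| 85 + 43 | 128 | 75.5% |
| 94 + 47 | 141 | 79.4% |
| 95 + 48 | 143 | 80.1% |
| 96 + 48 | 144 | 80.2% |
| 100 + 50 | 150 | 81.8% |

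**Step 4: the loss that 150 enrolled can bear.** (150 − 144)/150 = 6/150 = 4.0%. Taking 143 as the floor gives 7/150 = 4.7%.

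**Step 5: uneven loss.** The documents do not say how losses would divide between arms. If all 22 came from the active arm (78 + 50), power is 78.2%. If all 22 came from placebo (100 + 28), it is 64.1%. No division of 22 losses reaches 80%.

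**Step 6: detectable difference.** At 85 + 43 the difference detectable with 80% power is 528 mL, or 528/2000 = 26.4%, rather than 500 mL (25%).

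**Step 7: what adjustment could recover.** If model terms explain a share R² of the outcome variance, d becomes 0.5/√(1 − R²). The documents give no R², so these values are assumptions: at 85 + 43, R² of 0.1, 0.2 or 0.3 gives power of 79.8%, 84.2% or 88.7%.

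**The case against.** The strongest reply is that the trial as enrolled is not underpowered. With all 150 evaluable it has 81.8%, and it stays at or above 80% with six proportional losses. Heavy loss on this endpoint also looks unlikely. Section 11.4.2 makes the 24-hour value the primary measure, taken in hospital, so dropout before week 6 does not touch it. Section 11.3 makes the primary population everyone dosed. Section 10.3.5 lets the sponsor replace withdrawn patients. All of this stands, and it limits the practical risk, but none of it makes 14.7% the correct allowance. There is also some pull the other way: Section 8.1 counts a patient as analyzable only if all required assessments are completed, exclusion 16 in Section 8.3.2 concerns complications that arise during surgery, and enrolment is only up to about 150.

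A second reply is that Surgeon is already in the final model and may recover power. That is possible: a factor explaining about 10% of the variance would restore 80% at 85 + 43. But Section 11.2 neither claims nor quantifies such a gain, and it does not say whether the 1000 mL SD already excludes variation between surgeons. The 75.5% is therefore the unadjusted figure, on the same basis as the plan's own 128.

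On covariates, a model with treatment and Surgeon alone is valid in a randomised trial, so adding more is an improvement and not a correction. The documents do not show how strongly any baseline variable predicts blood loss. That part is fairly treated as secondary.

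**Conclusion.** The concern holds. The requirement in Section 11.2 is for equal arms and does not apply to a 2:1 trial. On the plan's own assumptions, power after the stated 14.7% loss is about 75.5%, some 4.5 points short of 80%, and the tolerable loss is about 4% (6 of 150). These figures assume a common SD of 1000 mL, a two-sample t-test without adjustment, and loss in proportion to allocation. The last assumption changes the size of the shortfall (64.1% to 78.2% at the extremes) but not its existence. The enrolled total of 150 is adequate if losses stay within that 4%. The error affects the stated power and margin; it does not affect the type I error or the validity of the estimate.

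**What to change.** **Section 11.2.** Replace the equal-arm statement with the 2:1 figures: 144 evaluable patients (96 active, 48 placebo) give 80% power; 150 give 81.8% with no loss; about 4% loss is tolerable; at 14.7% proportional loss power is about 75.5%. This changes wording only, and the declared margin becomes less favourable. If the sponsor wants to keep 80% power at 14.7% loss, the cost is enrolment: 144/(1 − 22/150) = 168.75, so 169 patients, or 171 (114 + 57) for an exact 2:1 split.

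**Section 11.4.2 (secondary, independent of the above).** Pre-specify baseline covariates alongside Surgeon. Pre-operative hematocrit and Nadler blood volume (or sex, height and weight) are natural choices, because they are collected already and enter the outcome formula in Section 10.5. The number of planned levels is another candidate, but it would have to be derived from the planned-procedure entry at screening, since the number of vertebrae fused is recorded only at surgery. Three covariates cost about 3 degrees of freedom. Any gain in power should be presented as an assumption unless the sponsor has data to support it.

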11.3. Populations for Analysis

Up to approximately 150 patients will be enrolled.

The primary analysis population will be a modified Intent to Treat (mITT) population consisting of all subjects receiving an injection of TXA or Placebo.

The secondary analysis population will be a Per Protocol (PP) population consisting of all subjects without major protocol violations (to be

determined by a blinded committee prior to breaking the double-blind code).

The safety population will consist of all subjects receiving an injection of TXA or placebo.

11.4. Statistical Analysis

11.4.1. General Approach

Data from multiple centers are intended to be combined under this protocol so that an adequate number of patients/subjects will be available for analysis.

Comparability of treatment groups based on demographic and baseline characteristics of the patients/subjects will be evaluated by appropriate statistical tests.

All hypothesis-testing analyses will be performed at the two-sided significance level of 5% ($\alpha=0.05$).

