7. TRIAL OBJECTIVES AND PURPOSE

The purpose of this study is to assess the efficacy and safety of tranexamic acid using a dosage regimen similar to that used in the currently approved indication (intravenous therapy of patients with hemophilia during and following tooth extraction) for the reduction of blood loss and minimizing transfusion rates in patients undergoing spinal fusion surgery. This study will be used to support registration and labeling of Exela's Tranexamic Acid products for use in the United States for this indication.

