8.2.2. Secondary Endpoints

The Secondary endpoints include assessment of:

1. Total Measured Blood Loss (measured intra-operatively and for up to 24 hours post-operatively and every 24 hours up to discharge when the two subfascial drains are removed). Total Measured Blood Loss will be estimated as 3 times cell saver.
2. Number of patients with symptomatic anemia (such as tachycardia, hypotension, presyncope) of <8.0 g/dL hemoglobin, or any hemoglobin <7.0 g/dL, precipitated transfusion. *[Alternatively, allogenic blood transfusion will be considered for hemoglobin <9 g/dL intraoperatively or <8 g/dL post-operatively]*
3. Number of patients with adverse events related to tranexamic acid such as confirmed deep vein thrombosis (DVT), pulmonary embolism (PE), or seizures.
4. Other outcomes will include functional recovery, duration of hospital stay, and wound complications (infections, hematomas, and other complications related with surgery).

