11.4.3. Analysis of Secondary Efficacy Endpoint(s)

Secondary efficacy variables will include the following.

1. Blood loss measured as 3 times cell saver.

Also included as secondary efficacy variables will be several outcomes normally treated as adverse events.

1. Incidence of symptomatic anemia as defined in Section 10.1.

Categorical secondary efficacy variables will be similarly analysed using multiple logistic regression analyses. If incidences are low, analyses of interaction effects may not be possible and Cochran-Mantel-Haenszel tests will be used instead.

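### Secondary efficacy variables are each tested at two-sided 5% with no gate on the primary and no order, so one could be declared significant after the primary fails

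*Combined protocol and SAP*

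**What the plan says.** Section 11.4.1 sets one level for every test: "All hypothesis-testing analyses will be performed at the two-sided significance level of 5" per cent.

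Section 11.4.2 makes the 24-hour value the primary blood-loss measure and lets later time points count only if that value is significant. It then says: "Due to the hierarchical structure of this analysis, no adjustment for multiplicity will be performed". That hierarchy concerns blood-loss time points only. The same section assigns ANCOVA to the continuous secondary variables.

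Section 11.4.3 names two secondary efficacy variables, blood loss taken as three times cell saver and the incidence of symptomatic anemia. It introduces the second with an open-ended sentence: "Also included as secondary efficacy variables will be several outcomes normally treated as adverse events". Categorical variables get logistic regression, or Cochran-Mantel-Haenszel tests if incidences are low. The section sets no precondition on the primary, no order and no split of alpha.

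Section 8.2.2 is wider. Besides those two it lists related adverse events (DVT, PE, seizures), and it adds: "Other outcomes will include functional recovery, duration of hospital stay, and wound complications". The word exploratory appears only for subgroup and covariance analyses (11.4.7 and 11.4.9).

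Section 7 gives the use of the results: "This study will be used to support registration and labeling of Exela's Tranexamic Acid products for use in the United States for this indication".

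**The concern.** A reader of 11.4.2 may take its no-adjustment sentence to cover the whole efficacy analysis. It does not: the hierarchy that justifies it orders time points of a single variable. Nothing in section 11 prevents a secondary variable from being declared significant at 5% after the 24-hour blood-loss test has failed.

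This matters mainly because of what the first secondary is. Total measured blood loss is a second measure of the quantity the primary measures by calculation. If the hematocrit-based primary failed and the cell-saver measure gave p < 0.05, the plan as written would let the result be presented as a significant reduction in blood loss. In a study intended for labeling, that should be settled before unblinding.

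The family is also not fixed. The plan does not say how many secondary tests will carry a claim, so the chance of a false one cannot be stated from the documents alone.

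**Working it through.** **The plan's own figure.** The only figure to reproduce is the sample size in 11.2, which starts from: "Assuming a two-sided alpha level of 0.05, 80% power and estimated mean blood loss of 2000 mL in the control group". The SD used there is 1000 mL. The stated result is: "a 25% decrease in blood loss in the treated group would require 128 patients (64 per group". The difference is 0.25 × 2000 = 500 mL, so d = 500/1000 = 0.5. The normal approximation gives n per group = 2(1.960 + 0.842)²/0.5² = 62.8, rounded up to 63. The t-test version gives 63.8, rounded up to 64, so 128 is reproduced. This confirms that two-sided 5% is the level used for the primary. It says nothing about the secondaries, for which the plan gives no error rate.

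**Inputs for the secondary family.**
- Level per test: two-sided 0.05 (11.4.1).
- Number of tests k: 2 (named in 11.4.3) up to 6 (outcomes in 8.2.2: measured blood loss, symptomatic anemia, DVT/PE/seizure as one item, functional recovery, hospital stay, wound complications).
- Correlation ρ between test statistics: not in the documents. Assumed common to all pairs, and varied from 0 to 0.8.
- All secondary nulls true (assumption).

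**Formula.** If independent, P(at least one false significant result) = 1 − 0.95^k. For k = 2 this is 1 − 0.9025 = 9.75%; for k = 6 it is 1 − 0.7351 = 26.5%. With correlation, write each statistic as √ρ·U + √(1−ρ)·E_i with U and E_i independent standard normal. Compute P(|Z| < 1.96 given U), raise it to the power k, average over U and subtract from 1.

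| | ρ = 0 | ρ = 0.5 | ρ = 0.8 |
|---|---|---|---|
| k = 2, either direction | 9.8% | 9.1% | 7.8% |
| k = 6, either direction | 26.5% | 20.7% | 13.9% |
| k = 2, favouring TXA only | 4.9% | 4.5% | 3.9% |
| k = 6, favouring TXA only | 14.1% | 10.4% | 6.9% |

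The last two rows count only Z beyond 1.96 in the favourable direction; at ρ = 0 they are 1 − 0.975² and 1 − 0.975⁶.

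**The substitution scenario.** With the primary also null and the same common correlation, the chance of a favourable significant secondary without a favourable significant primary is:

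| | ρ = 0.5 | ρ = 0.8 |
|---|---|---|
| Cell-saver measure alone | 2.0% | 1.4% |
| Either of the two named variables | 3.8% | 2.4% |

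Under a rule that tests secondaries only after a significant primary, a secondary claim after a failed primary cannot occur.

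**Why a gate alone is not enough.** If TXA truly lowers 24-hour blood loss, the gate usually opens, and the two secondaries are then exposed to roughly the unadjusted 8% to 10%. A fixed order that stops at the first non-significant result keeps the chance of any false claim along that sequence at or below 5%, whatever the correlation.

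**The case against.** The strongest reply is that 11.4.1 sets a per-test level, that no section promises a family-wise level for the secondaries, and that no section makes a secondary result a criterion for success. All of this is true. A reader might infer that the plan promises 5% over the secondary family and misses it; the documents do not support that.

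A reader might also take six tests as the family and quote an error of 21% or more. That is not established either. Section 11.4.3 names two variables. Section 10.6 lists functional recovery, wound complications and hospital stay among the safety assessments, and the DVT/PE/seizure item may belong to the Fisher tests of 11.4.4. On the other side, 10.5 repeats the whole list under secondary efficacy objectives, and 11.4.3 speaks of several outcomes. Six is therefore the widest reading, not the plain one. A single figure such as 21% also depends on an assumed correlation of 0.5.

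Third, two-sided rates overstate the risk of a false efficacy claim, because half of the false results under the null favour placebo. For the specific fear, a cell-saver result replacing a failed primary, the chance is about 1% to 2% at correlations of 0.5 to 0.8. That stands and limits the size of the point.

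Finally, the sponsor could simply call the secondaries supportive, with no formal claim. That would meet the concern too, but the plan does not say it.

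**Conclusion.** The gap is real and modest. As written, either secondary variable named in 11.4.3 can be declared significant at two-sided 5% whatever happens to the primary, and the hierarchy in 11.4.2 does not prevent it. For those two variables the chance of at least one false significant result is about 8% to 10% in either direction, and about 4% to 5% in favour of TXA. On the widest reading of 8.2.2 the two-sided figure is about 14% to 26%.

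These figures assume that every secondary null is true and that the statistics share a common correlation between 0 and 0.8. If some effects are real, fewer nulls are true and the chance is lower. The primary test itself is not affected. This is a cheap improvement, not a flaw that undermines the trial.

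**What to change.** Keep the time-point rule in 11.4.2, and limit its no-adjustment sentence to that rule. Add to 11.4.3:

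> Secondary efficacy variables will be tested for significance only if the primary test (24-hour total blood loss, section 11.4.2) is significant at two-sided 0.05, in the fixed order (1) total measured blood loss, (2) incidence of symptomatic anemia, each at two-sided 0.05, stopping at the first non-significant result. Later blood-loss time points, functional recovery, hospital stay and wound complications support no claim beyond the 11.4.2 rule and are reported, like adverse-event comparisons, with estimates, 95% CIs and nominal p-values.

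Narrow the sentence in 11.4.1 so that the 5% level applies to the primary test, the 11.4.2 rule and this sequence.

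Two limits should be noted. The 5% bound covers the primary followed by the two secondaries; later time points remain under their own rule and are not part of that bound. And 8.2.1 also lists transfusion incidence as a primary endpoint, while 11.4.2 treats total blood loss as the primary variable. If transfusion incidence stays primary, its place in the gate must be stated when that separate issue is resolved.

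The cost is protocol and SAP wording before unblinding, with no extra patients or data. The downside is that a secondary result cannot be claimed as significant if the primary or an earlier secondary fails.
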